6.5.2 Secondary Objectives Analyses

For the secondary aim, which is to examine differences by flavor for outcomes at each water concentration, we will examine at each water concentration, flavor as the within subject factor and each of the measure (e.g. irritation, appeal) as outcomes in separate models. We will construct confidence intervals for least square means and contrasts between least square means to estimate effect sizes and to inform future studies.

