4.3 Secondary Objectives (if applicable)

At each water concentration, we will examine if there are differences in perception of sensory irritation and appeal across the distinct aldehyde containing flavors.

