5.2.2 Secondary Outcome Variables (if applicable)

- (2)** At each water level, differences in **irritation** and **appeal** between flavors (to examine if there are differences in effect of water level on irritation/appeal by aldehyde flavor)

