6.1.4 Method of Assignment/Randomization

All participants will receive every flavor/water concentration (4 e-liquids flavors at 4 water concentrations = 16 total manipulations). Participants and research assistants will be blinded to flavors administered. We will use block randomization to determine order flavors are presented in. Water concentration will be presented from hypothesized least irritating to most irritating (20% water, 10% water, 5% water, no alteration).

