6.4 Statistical Method

6.4.1 Statistical Design

To examine the primary objective of the study, which is to examine how increasing the concentration of e-liquids with aldehyde flavor chemicals impacts sensory perception of irritation and appeal among current adult e-cigarette users, we will use mixed effects models with water concentration as the within subject factor and each of the measure (e.g. irritation, appeal) as outcomes in separate models. Outcome analyses will be intent-to-treat and using mixed-effects models. These models allow for different numbers of observations per subject, use all available data, and can handle missing-at-random data. If model assumptions will appear to be violated, we will transform the data or fit more flexible generalized linear or nonparametric mixed models. A significant main effect of condition will be considered supportive of our hypothesis. We will construct confidence intervals for least square means and contrasts between least square means to estimate effect sizes and to inform future studies.

For the secondary aim, which is to examine differences by flavor for outcomes at each water concentration, we will examine at each water concentration, flavor as the within subject factor and each of the measure (e.g. irritation, appeal) as outcomes in separate models. We will construct confidence intervals for least square means and contrasts between least square means to estimate effect sizes and to inform future studies.

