6.4.2 Sample Size Considerations

Given this is a pilot study, formal power analyses were not conducted. However, based on prior pilot data in which brief lab exposure to e-cigarettes were conducted by our group (HIC 2000025687) determined that 30 participants is sufficient to detect large differences of irritation and appeal by water concentration at two sided alpha level of 0.05.

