6.5 Planned Analyses

6.5.1 Primary Objective Analysis

To examine the primary objective of the study, which is to examine how increasing the concentration of e-liquids with aldehyde flavor chemicals impacts sensory perception of irritation and appeal among current adult e-cigarette users, we will use mixed effects models with water concentration as the within subject factor and each of the measure (e.g. irritation, gLMS and appeal, LHS) as outcomes in separate models. A significant main effect of condition will be considered supportive of our hypothesis. We will construct confidence intervals for least square means and contrasts between least square means to estimate effect sizes and to inform future studies.

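### The secondary outcome is meant to show whether water's effect differs by aldehyde flavor, but the plan specifies no flavor-by-water contrast, interval or test

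*Combined protocol and SAP*

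**What the plan says.** **Purpose of the outcome.** The synopsis (Secondary and Exploratory Outcome Variables) and section 5.2.2 define the secondary outcome as flavor differences in irritation and appeal at each water level. Both add a bracketed purpose: "to examine if there are differences in effect of water level on irritation/appeal by aldehyde flavor".

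**Objective.** Section 4.3 is narrower. At each water concentration, "we will examine if there are differences in perception of sensory irritation and appeal across the distinct aldehyde containing flavors".

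**Secondary analysis.** Section 6.5.2 states that "we will examine at each water concentration, flavor as the within subject factor and each of the measure" will be analysed, and the second paragraph of 6.4.1 says the same. Section 6.5.2 adds: "We will construct confidence intervals for least square means and contrasts between least square means to estimate effect sizes". The only factor named there is flavor.

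**Primary analysis.** In 6.5.1, "we will use mixed effects models with water concentration as the within subject factor". No flavor term is named.

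**Elsewhere.** Exploratory analyses (6.5.3) and other analyses (6.5.8) are marked not applicable.

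**Design and size.** Section 6.1.4: "All participants will receive every flavor/water concentration", which is 4 flavors by 4 levels, or 16 conditions. The target is 30 participants. Section 6.4.2: "Given this is a pilot study, formal power analyses were not conducted".

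**The concern.** Whether water acts differently in cherry, vanilla and cinnamon is a question about differences between flavors in a change across water levels. The plan names flavor within a level, or water alone, but never the two together.

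A flavor difference at a single level mixes two things: how irritating or appealing that flavor is anyway, and any difference in how it responds to water. To separate them, the by-level differences must be compared across levels, and the plan does not say how to do that or how to attach an interval. A reader may then compare which levels reached significance, and that pattern can vary when water acts identically in every flavor.

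At stake is the usefulness of this pilot for the purpose in 5.2.2. The plan says its contrasts are there to estimate effect sizes and inform later studies, and this effect is not among those specified.

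**Working it through.** **1. Sections side by side.**

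| Section | Factor named | Question answered |
|---|---|---|
| 4.3 | flavor, at each level | do flavors differ at this level? |
| 5.2.2 and synopsis, in brackets | water effect, by flavor | does water's effect differ by flavor? |
| 6.4.1 (second paragraph), 6.5.2 | flavor, at each level | same as 4.3 |
| 6.4.1 (first paragraph), 6.5.1 | water | does water matter? |

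Row 2 has no matching analysis.

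**2. The plan's own figure.** Section 6.4.2 calls 30 participants sufficient for large differences by water concentration at two-sided 0.05. It gives no power, SD or effect size, so the figure cannot be reproduced. It is plausible for a simple paired contrast: at n=30 the power is 0.75 for a standardized paired difference of 0.5 and 0.99 for 0.8. It says nothing about a difference in water effect.

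**3. Precision of the missing contrast.** All inputs are assumptions: total SD 1, n=30, equal correlation 0.5 between a participant's ratings (range 0.3 to 0.7), so the error variance is 0.5 (0.7 to 0.3).

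- By-level flavor contrast: variance 2 × (participant-by-flavor + error variance). Expected half-width = 2.045 × √(2 × 0.5/30) × 0.991 = 0.37 SD. Here 2.045 is the t quantile on 29 df and 0.991 converts to the expected sample SD.
- Two-flavor difference in native-to-20% change: variance 4 × error variance. Half-width = 2.045 × √(4 × 0.5/30) × 0.991 = 0.52 SD. It is 0.62 with error variance 0.7 and 0.41 with 0.3.

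**4. What by-level intervals reveal.** Hold the by-level half-width at 0.37 SD (variance sum 0.5) and vary its make-up.

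| Participant-by-flavor / error variance | Correct half-width | Two by-level intervals combined as independent | Coverage of the combination |
|---|---|---|---|
| 0 / 0.50 | 0.52 | 0.53 | 95% |
| 0.20 / 0.30 | 0.41 | 0.53 | 99% |
| 0.25 / 0.25 | 0.37 | 0.53 | 99% |

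The combination is about right in the first row and 42% too wide in the last. The same by-level output fits all three.

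**5. Comparing significance by level.** In 2,000 simulated trials (residual and participant SD 1, flavors shifted by 0, 0.3 and 0.6, identical water effects), the four by-level flavor tests gave a mix of significant and non-significant results in 88% of trials. With shifts of 0, 0.4 and 0.8 the figure was 63%. The interaction test rejected in 4–5%.

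**6. Power of the interaction test.** There are (3−1) × (4−1) = 6 numerator df and 29 × 6 = 174 denominator df. Suppose water effects at 20% of 0, −0.4 and −0.8 SD, reached in equal steps over the four levels. The squared interaction effects sum to 0.32 × 0.5556 = 0.1778, and the noncentrality is 30 × 0.1778/0.5 = 10.7. Power is 66% (49% at correlation 0.3, 90% at 0.7). With effects half as large it is 18% (14% to 29%). The interval is therefore the main product.

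**7. Which model.** With participant, participant-by-flavor and cell effects only, the residual has 360 − 1 − 11 − 29 − 58 = 261 df and absorbs any variation between participants in their overall response to water. I simulated this with participant-by-flavor, participant-by-water and error variances of 0.25 each (assumed). That model gives a half-width of about 0.51 SD where 0.36–0.37 is correct. Its interaction test rejects in about 0.1% of null trials, against about 5% once participant-by-water is added. By-level contrasts taken from it widen from 0.37 to about 0.43 SD. Per-participant paired contrasts avoid the problem, because both participant-by-flavor and participant-by-water effects cancel in the double difference.

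**The case against.** **The by-level analysis is what the secondary objective asks for.** This stands. Section 4.3 and the aim as restated in 6.4.1 and 6.5.2 agree with the planned models. A reader might infer that the secondary objective has no valid analysis; the documents do not support that. The mismatch is with a bracketed purpose, although one stated twice.

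**The promised contrasts might cover it.** In 6.4.1 and 6.5.2 the phrase about separate models can be read as applying to measures rather than to water levels. By-level contrasts could then come from one joint model that holds the cross-level covariance. That reading is open, so it would be too strong to say that precision is unrecoverable. Even so, the text names flavor alone and promises no contrast across levels.

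**By-level output is not useless.** With complete data, subtracting by-level contrasts gives a point estimate. If flavor differences correlate non-negatively across levels, combining two by-level intervals gives a conservative bound (95–99% coverage above). A reader might infer that the plan leaves no measure of precision, or that it leads to false claims. Neither follows: the cost shown for this route is an interval up to 42% too wide. The misleading pattern in step 5 arises only if someone compares significance across levels, which the plan does not prescribe.

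**It is a pilot without a power analysis.** True, and it lowers the severity. It also favors an interval over a test, which is what the fix puts first.

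**Conclusion.** The gap is real and narrow. The purpose stated in the synopsis and 5.2.2 has no specified contrast, interval or test, while objective 4.3 is properly served. Comparing by-level results across levels gives at best a point estimate with a rough, usually conservative, bound.

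That conclusion rests on the text alone. The sizes rest on assumed SDs, correlations and effects, because the documents give none: a half-width of about 0.5 SD (0.4 to 0.6) for the added contrast, and interaction power of about 66% for a 0.8 SD spread in water effects or 18% for 0.4 SD.

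The severity is modest. This is a cheap improvement to a secondary outcome of a pilot, and it does not affect whether the trial can proceed.

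**What to change.** **Keep** the by-level flavor contrasts for 4.3 as planned. Do not re-derive them from a model that lacks a participant-by-water effect.

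**Add** to 6.4.1 (second paragraph) and 6.5.2, for the purpose in 5.2.2:

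- For each outcome, report the pairwise differences between cherry, vanilla and cinnamon in the native-to-5%, native-to-10% and native-to-20% change, with 95% CIs.
- Compute them from per-participant paired contrasts, or from one mixed model per outcome with flavor, water and flavor-by-water as fixed effects and random participant, participant-by-flavor and participant-by-water effects.
- Report the 6-df interaction test (6 and 174 df with complete data) as support only.
- Report the 5%-to-20% change alongside. Section 6.1.3 measures native water content container by container, so it may differ by product, whereas 5% to 20% spans the same 15 points in every flavor.
- State that water order is fixed (6.1.4; 6.3, Lab Visits). An order effect common to all flavors cancels in these differences; a flavor-specific one does not.

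**Or**, if the interaction is not wanted, delete the bracketed clause from the synopsis and 5.2.2 so that outcome and analysis agree.

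**Cost.** Wording and model code only, since all 16 conditions are already given to every participant. The downsides are nine more intervals per outcome (3 flavor pairs × 3 changes), three more for the 5%-to-20% check, and one more test. All should be labelled as unadjusted pilot estimates with limited precision at n=30.

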6.5.3 Exploratory Objectives Analyses (if applicable)

N/A

6.5.4 Safety

See 6.1.2 for treatment of adverse events.

6.5.5 Analysis of Subject Characteristics

Participant demographics, tobacco product history, e-cigarette history, and e-cigarette dependence level will be collected at intake and used to characterize population. All participants will receive the same treatment (within subject design).

6.5.6 Interim Analysis (if applicable)

N/A

6.5.7 Health economic evaluation

N/A

6.5.8 Other

N/A

6.5.9 Subsets and Covariates

Given this is a pilot trial, we do not have apriori defined associations between subject characteristics and response to change in water concentration. Additionally, as this is a within subject design subject characteristics that influence e-cigarette perception (i.e. menthol status, heaviness of e-cigarette use, prior flavor experience) are likely not to impact analyses.

6.5.10 Handling of Missing Data

Outcome analyses will be intent-to-treat and using mixed-effects models. These models allow for different numbers of observations per subject, use all available data, and can handle missing-at-random data. If model assumptions will appear to be violated, we will transform the data or fit more flexible generalized linear or nonparametric mixed models.

7 Trial Administration

7.1 Ethical Considerations: Informed Consent/Accent and HIPAA Authorization

The study will be conducted in accordance with the conducted in accordance with the ethical principles that have their origin in the Declaration of Helsinki.

Participants will not be told of the flavors administered, the water concentration administer, or the nicotine concentration of the product. They will be told that products containing moderate levels of nicotine, flavorings that do or do not contain components considered "flavor aldehydes" and that we will be adding water to some of the formulations they will be trying. We will inform participants of this in the consent and indicate that we do not plan to tell them as we do not want prior perceptions of nicotine content or flavors to influence their experience with the product. Participants will be asked not to sign consent if they are uncomfortable with this.

Participants will be compensated \$50 for completing both parts of intake (\$30 for remote portion, \$20 for in person portion). This is commensurate to other e-cigarette studies in our labs. Participants will be compensated \$75 for each laboratory session that is approximately 2 hours in length. Additionally, participants are asked to abstain from vaping for 2 hours prior to each lab session, so this compensation is included. Additionally, at in person appointments, participants will be compensated for travel with \$25. This is the equivalent of the cost of a rideshare in the greater New Haven area to and from our appointment space. Given the short duration of the study and participant preference in previous vaping studies, all compensation will be provided in cash.

The only potential unknown condition identified by the study team that could be discovered as a result of study procedures would be EVALI, due to increased health monitoring for EVALI symptoms. This is included as an added study benefit. During the study, they will be monitored for EVALI related symptoms. Any endorsement of EVALI symptoms that does not have a clear related and proximal cause will result in withdrawal and participants will be referred to a primary care provider.

No information from this study will be added to participant medical records.

7.2 Institutional Review Board (IRB) Review

The protocol will be submitted to the IRB for review and approval. Approval of the protocol must be obtained before initiating any research activity. Any change to the protocol or study team will require an approved IRB amendment before implementation. The IRB will determine whether informed consent and HIPAA authorization are required.

The IRB will conduct continuing review at intervals appropriate to the degree of risk, but not less than once per year.

A study closure report will be submitted to the IRB after all research activities have been completed.

Other study events (e.g. data breaches, protocol deviations) will be submitted per Yale's IRB's policies.

7.3 Subject Confidentiality

Subject confidentiality is held in strict trust by the research team. Subject medical record review will be limited to the just the elements needed to complete the study. Only authorized HIPAA and GCP trained study team members will be allowed to collect data for this project. No direct subject identifiers will be entered into study tracker.

Each subject will be assigned a unique study number that is not linked to their identifying information. A master list linking the unique study number to the human subject will be maintained in a locked drawer in PI's office and on an encrypted document on a secure server. Only study staff will have access to this document.

7.4 Deviations/Unanticipated Problems

If the study team becomes aware of an anticipated problem (e.g. data breach, protocol deviation), the event will be reported to the IRB by PI within 24 hours of being aware of event if necessary. Protocol deviations will be documented in Study Deviation Tracker.

7.5 Data Collection

Data will be collected via surveys and questionnaires listed in the Visit Schedule table above. No licensure is required for any administration and all questionnaires will be administered by research assistants who have been trained in administration of sensory tasks. All data will be collected either via paper forms or via Redcap (CRF 11 compliant) with the exception of the gLMS and LHS, which will be collected on custom software for quantification of subjective responses. The data will be downloaded on a monthly basis from Redcap and stored on a secure server. Any paper data will be stored in a locked file cabinet. Data will be stored this way for 7 years after the final data is collected. After this point, the Principal Investigator will oversee the process in which data is destroyed or de-identified.

7.6 Data Quality Assurance

All data forms will be identified with the study ID of the participant and include date/time and study visit. The codes that link the name of the participant and the study ID will be kept confidential by the Principal Investigator in a secured cabinet. Online data will be downloaded on a monthly basis from Redcap and stored on a secure server. Error checking and data validation will occur weekly and any problems will be queried and resolved immediately. [name] will receive monthly data quality reports to check for completeness and accuracy of key demographic and prognostic variables, as well as rates of recruitment and retention..

Multiple measures are in place to ensure the validity and integrity of the data. First, all research staff receive Human Subjects Protection and Good Clinical Practice training. Second, formal training in clinical assessments and procedures will be conducted to ensure quality of the data and help implement and improve recruitment strategies so that enrollment goals are achieved. Third, weekly research staff meetings take place, as a forum for in-service training as well as to discuss questions regarding issues that arise in the research protocols. Lastly, adherence to assessment administration will be monitored and if research drift is observed, the research assistants will be re-trained.

7.7 Study Records

Study records are considered protocol, consents, and survey/questionnaires collected as part of the study procedures. No medical records are collected as part of this study.

7.8 Access to Source Documents

Source documents include paper and Redcap data collected as a part of the study. Online data will be downloaded on a monthly basis from Redcap and stored on a secure server. Paper data will be stored in a locked cabinet.

7.9 Data or Specimen Storage/Security

The majority of data for this study will be collected, recorded and stored using REDCap (Research Electronic Data Capture). REDCap is a secure, web application designed to support data capture for research studies. It includes features for HIPAA compliance including real-time data entry validation (e.g. for data types and range checks), a full audit trail, user-based privileges, de-identified data export mechanism to statistical packages (SPSS, SAS, Stata and R), and integration with the institutional Active Directory. Access to study data in REDCap will be restricted to the members of the study team with authentication through University NetID credentials.

The REDCap@Yale database and web server are housed on secure platforms that are backed up daily. REDCap@Yale meets the security standards for use with high risk data as set forth by the [Yale Information Security Office](#).

Identifying information (consent, contact information) will be collected on paper documents and stored in a locked cabinet and/or uploaded to secure server and encrypted.

All participants will be assigned a Study ID following consent and all study documents will use that ID.

7.10 Retention of Records

The data will be downloaded on a monthly basis from Redcap and stored on a secure server. Any paper data will be stored in a locked file cabinet. Data will be stored this way for 7 years after the final data is collected. After this point, the Principal Investigator will oversee the process in which data is destroyed or de-identified.

7.11 Study Monitoring

The principal investigator and study team are responsible for monitoring the data, assuring protocol compliance and conducting the safety reviews. Study monitoring will occur weekly. The study team, in consultation with the Yale TCORS Independent Data Safety Monitoring Board (DSMB), will evaluate adverse events and determine whether the adverse event affects the Risk/Benefit ratio of the study and whether modifications to the protocol or consent form are needed. Reviews will be held every 6 months.

